### **6.3 Handling of efficacy endpoints if rescue therapy is performed**

If rescue therapy is performed, data from the day after rescue therapy should not be used to assess efficacy.

## 6.4 Imputation of missing values

The mixed repeated-measures model (MMRM) used to analyze the primary efficacy endpoint should not use data imputing missing data. If there are missing values at the first day of the treatment period, data from the day closest to the first day of the treatment period should be used as data for the first day of the treatment period.

For the primary endpoint, the mean Hb levels at Weeks 20 and 24 of the treatment period, missing data are imputed with data from the evaluation period immediately before the missing evaluation period (excluding the first day of the treatment period) (LOCF method). When any one evaluation time points has missing values, the data at the evaluation time point closest to the missing evaluation time point is adopted, and when two evaluation time points have missing values, the data in the two different evaluation time points closest to and before the missing evaluation time points should be adopted to calculate the mean Hb value. However, Hb values at the same evaluation time point should not be used.

In addition, clinical laboratory values, vital signs, and QOL indices among the efficacy endpoints, values imputed by the LOCF method at Week 24 of the treatment period should also be output. Data of Week 24 of the treatment period imputed with missing values will be used as data from the completion of treatment period.

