9.2.3 Efficacy endpoints

Blood sampling will be performed at each study center for measurement by the contract laboratory testing facility. Study centers will store test reports issued by the contract testing laboratory.

During the screening period, blood will be collected before dialysis whenever the subject makes a study visit on the same day they are scheduled for dialysis. During the treatment period, blood will be collected before dialysis on days the subject is scheduled for dialysis.

(1) Hb value

Blood sampling and Hb measurement will be performed in the supine position on the first day of the screening period, screening period Visit 2, the first day of the treatment period, Weeks 2, 4, 6, 8, 10, 12, 16, 20, and 24 of the treatment period, and the day of discontinuation of treatment.

(2) Ratio of subjects who received ESA rescue therapy

If ESA rescue therapy is performed, type of ESA formulation used, administration route, dose interval, and dosage will be recorded in the CRF.

(3) Ratio of subjects who received red blood cell (RBC) transfusion rescue therapy.

If RBC transfusion rescue therapy is performed, type of RBC formulation used and dosage will be recorded in the CRF.

(4) Study drug dosage

Study drug dosage will be recorded in CRFs.

(5) Total number of dosage adjustments

Yes/no for study drug dosage adjustments and post-adjustment dosage will be recorded in the CRF.

(6) Quantity of iron administered

Iron dosage will be recorded in CRFs.

(7) Iron-related measures (serum iron, TIBC, TSAT, and serum ferritin)

Blood sampling and measurement will be performed for serum iron, TIBC, TSAT, and serum ferritin on the first day of the screening period, the first day of the treatment period, Weeks 2, 4, 6, 8, 10, 12, 16, 20, and 24 of the treatment period, and the day of discontinuation of treatment.

(8) Hepcidin

Blood sampling and measurement of hepcidin will be performed on the first day of the treatment period, treatment period Weeks 2, 4, 6, 12, and 24, and the day of discontinuation of treatment.

(9) Haematocrit, RBC count

Blood sampling and measurement will be performed for haematocrit and RBC count on the first day of the screening period, the first day of the treatment period, Weeks 2, 4, 6, 8, 10, 12, 16, 20, and 24 of the treatment period, and the day of discontinuation of treatment.

(10) Reticulocytes (counts and fractions)

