Blood sampling and measurement will be performed for reticulocytes (counts and fractions) on the first day of the screening period, the first day of the treatment period, Weeks 2, 4, 6, 8, 10, 12, 16, 20, and 24 of the treatment period, and the day of discontinuation of treatment.

(11) EPO

Blood sampling and measurement of EPO will be performed on the first day of the treatment period, treatment period Weeks 2, 4, 6, 12, and 24, and the day of discontinuation of treatment. Blood sampling time will be recorded in CRFs.

(12) QOL measures (EQ-5D-5L, KDQOL)

Subjects will fill out EQ-5D-5L and KDQOL questionnaires (Appendices 4 and 5) on the first day of the treatment period, treatment period Weeks 12 and 24, and the day of discontinuation of treatment, and results recorded in CRFs.

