5) Vascular endothelial growth factor (VEGF)

Blood sampling and measurement of VEGF will be performed on the first day of the screening period, treatment period Weeks 12 and 24, and the day of discontinuation of treatment.

(2) Resting standard 12-lead ECG

Resting standard 12-lead ECG will be measured in the supine position during hospital visits on the first day of the treatment period, treatment period Week 24, and the day of discontinuation of treatment. ECG diagnosis consists of a comprehensive evaluation including arrhythmia and wave-form diagnoses.

Measured to extent possible prior to blood sampling before dialysis on the day of dialysis. Measurements will be made before blood sampling when possible, and after 5 minutes at rest.

- 1) Normal
- 2) Clinically non-problematic abnormality
- 3) Clinically problematic abnormality

(3) Dry weight

Dry weight will be measured during study visits on the first day of the treatment period, treatment period Weeks 12 and 24, and the day of discontinuation of treatment. Measurements are recorded in CRFs.

(4) Body weight

Body weight will be measured before and after dialysis during study visits on the first day of the treatment period, treatment period Weeks 12 and 24, and the day of discontinuation of treatment. Measurements are recorded in CRFs.

(5) Duration of hemodialysis

The duration of hemodialysis during visits on the first day, Week 24 of the treatment period, and on the day of treatment discontinuation should be recorded in CRFs.

(6) Vital signs

Sitting blood pressure and pulse rate will be measured during study visits on the first day of the treatment period, treatment period Weeks 2, 4, 6, 8, 10, 12, 16, 20, and 24, and the day of discontinuation of treatment.

During the screening period, measurements will be made before dialysis whenever the subject makes a study visit on the same day they are scheduled for dialysis. During the treatment period, measurements will be made before dialysis on days the subject is scheduled for dialysis. Measurements will be made before blood sampling when possible, and after 5 minutes at rest.

(7) Fundoscopy

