### **6.2 Handing of data for tabulation at each evaluation time point**

Data that meet the permitted range specified in the “Table 9.1-1 Permitted range of study visits” section of the protocol should be used for the tabulation at each evaluation time point and should not be imputed with those outside the permitted range.

If there are multiple data within the permitted range, then the one closer to the reference date should be adopted. If the deviations from the reference date are the same, data for the efficacy and safety evaluations should be adopted before and after the reference date, respectively.

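### The SAP's rule for a missing first-day value is not limited to pre-dose data, so an on-treatment value can become the baseline

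*SAP*

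**What the plan says.** SAP 6.4 provides that, where the first-day value is missing, "data from the day closest to the first day of the treatment period should be used" in its place. It gives no direction in time and no maximum distance. For the Week 20 and Week 24 LOCF the same section does give a direction: when both visits are missing, the values "closest to and before the missing evaluation time points should be adopted".

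The sentence just before the baseline rule states that the MMRM "used to analyze the primary efficacy endpoint should not use data imputing missing data". It does not say whether a substituted first-day value counts as imputed.

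SAP 6.2 adds that visit data "should not be imputed with those outside the permitted range", and that when two values are equally distant, efficacy takes the earlier one. Protocol Table 9.1-1 gives the first day no permitted range. The protocol's own imputation rule (13.2(4)) covers Week 24 only, and SAP section 9 does not list the baseline rule as a change from the protocol.

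The first-day value is the MMRM covariate (SAP 7.5.1(1)) and the reference for all changes from the first day. It also decides who enters the time-to-target analysis: subjects with a first-day Hb of 10.0 g/dL or more are left out (SAP 7.5.1(4)).

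**The concern.** A baseline is meant to describe the subject before treatment. Read literally, this rule picks an on-treatment value whenever that value lies nearer to Day 0 than the last pre-dose one. For some measures the schedule offers no pre-dose alternative.

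The consequences for an affected subject are these:

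- The change at the visit whose value was borrowed is zero by construction.
- Every later change is measured from a point already on treatment. For a measure that responds to the drug, this biases the change toward no effect.
- In the MMRM the same number serves as both covariate and response.
- A borrowed Hb of 10.0 g/dL or more removes the subject from the time-to-target analysis, and that subject would be an early responder.

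**Working it through.** The documents give no figure on this point to reproduce. The check has two parts: which value the rule selects, and what that selection does to the change.

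**Which pre-dose values exist** (protocol 9.2.3, taking the text as governing)

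| Measure | Scheduled pre-dose assessments besides the first day | Next scheduled visit on treatment |
|---|---|---|
| Hb | SV1 and SV2 (day of SV2 not fixed) | Week 2 |
| Iron indices, hematocrit, RBC count, reticulocytes | SV1 | Week 2 |
| Hepcidin, EPO | none | Week 2 |
| EQ-5D-5L, KDQOL | none | Week 12 |

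For hepcidin the text reads "Blood sampling and measurement of hepcidin will be performed on the first day of the treatment period", followed by treatment visits only. The QOL questionnaires are completed "on the first day of the treatment period, treatment period Weeks 12 and 24, and the day of discontinuation of treatment". For these measures any scheduled substitute is on-treatment. It would normally be the visit shown, or a discontinuation visit if that came earlier.

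**When Week 2 beats a screening value.** Let g be the days from the last pre-dose sample to Day 0, and w the day of the Week 2 visit. Table 9.1-1 allows w from 11 to 17, and screening may last up to 6 weeks, so g can reach 42. The rule selects Week 2 when g > w:

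- w = 11: g from 12 to 42 days
- w = 14: g from 15 to 42 days
- w = 17: g from 18 to 42 days

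For Hb, g is counted from SV2 or any later re-test. For the measures sampled at SV1 only, it is counted from SV1 unless a re-test was done.

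**Size for Hb.** The documents give no rate of rise, so I assume a linear rise of r = 0.1 to 0.5 g/dL/week. The early response lost from each later change is r × w / 7. With N = 20 (protocol 6.1), one affected subject lowers the mean change by that amount divided by 20. With w = 14:

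| r (g/dL/week) | Lost per subject | Shift in mean, 1 of 20 | Week 2 change, true → recorded | Week 4 change, true → recorded |
|---|---|---|---|---|
| 0.10 | 0.20 | 0.010 | 0.20 → 0.00 | 0.40 → 0.20 |
| 0.25 | 0.50 | 0.025 | 0.50 → 0.00 | 1.00 → 0.50 |
| 0.50 | 1.00 | 0.050 | 1.00 → 0.00 | 2.00 → 1.00 |

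All figures are in g/dL except r. Over w = 11 to 17, the loss per subject runs from 0.1 × 11/7 = 0.16 to 0.5 × 17/7 = 1.21 g/dL. Three affected subjects at w = 14 would lower the mean by 0.03 to 0.15 g/dL.

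**Responder endpoint.** As an illustration, take a true first-day Hb of 9.0, a Week 2 Hb of 9.5 and a later Hb of 10.3 g/dL. The true change is 10.3 − 9.0 = 1.3, which meets the 1.0 g/dL threshold. With the borrowed baseline it is 10.3 − 9.5 = 0.8, which does not. One subject in 20 is 5 percentage points.

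**Under a pre-dose rule.** Hb falls back to SV2 or SV1, and the SV1-only measures fall back to SV1. Hepcidin, EPO and QOL have no scheduled fallback, so their baseline stays missing.

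**The case against.** The strongest case on the other side is that this is a wording gap with little practical reach.

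- **The trigger should be uncommon.** First-day tests are done before the first dose, and results are reviewed before the treatment period starts (protocol 8.2.3 and 8.3). The rule acts mainly on an omitted test or an invalid sample. This stands. No frequency is given, so the practical size cannot be fixed.
- **The primary estimate is hardly touched.** A reader might infer that the main result is biased. Mean Hb at Weeks 20 and 24 is an absolute level, and baseline enters only as a covariate with one common slope. With complete data and LSMeans taken at the mean covariate, the baseline term averages to zero and the LSMeans equal the raw visit means. A wrong covariate value then affects precision, not the estimate; with dropouts there is a small effect. The bar on imputed data may also exclude the substituted value, though SAP 6.4 does not say so. This stands.
- **Hb is the less exposed measure.** It is sampled at SV1 and SV2, and re-testing can add later values. A reader might infer that Week 2 is often or always chosen. Six weeks is a maximum, no typical screening length is given, and a discontinuation or unscheduled value may be nearer than the scheduled visit.
- **The change is not cancelled throughout.** It is zero only at the borrowed visit; later changes are reduced. The regression slope excludes subjects without first-day data (SAP 4.12), so it is largely protected.
- **ECG is a reading of scope.** The protocol text says "Resting standard 12-lead ECG will be measured in the supine position during hospital visits on the first day of the treatment period" and schedules no screening ECG, so a borrowed Week 24 result would show no shift by construction. But the baseline sentence sits beside one on the primary MMRM, and ECG is not named in SAP 6.4. The documents do not establish that a safety change would be hidden.

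None of this supplies the missing direction. The tie rule in SAP 6.2 needs equal distances, and its window rule has nothing to act on because the first day has no window. The requirement to test before dosing governs when first-day tests are done, not what replaces a missing one.

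**Conclusion.** The point holds, with limited reach. Followed as written, SAP 6.4 gives an on-treatment baseline for hepcidin, EPO and QOL whenever the first-day value is missing and only scheduled data exist. It does the same for iron indices, hematocrit, RBC count and reticulocytes when the last pre-dose sample lies further from Day 0 than Week 2. For Hb this requires SV2 and any re-test to be that far back.

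For Hb the size is small: 0.01 to 0.05 g/dL on the mean change per affected subject in 20, and possibly 5 percentage points on the responder rate. These figures assume a linear rise of 0.1 to 0.5 g/dL/week and Week 2 at Day 14. For the other measures the documents give nothing from which to compute a size. The effect on the estimate of mean Hb at Weeks 20 and 24 is likely negligible. The shift-table issue for ECG arises only if the rule is read to cover ECG.

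The sentence should still be corrected, because it prescribes a wrong result in a foreseeable case and the correction is cheap.

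**What to change.** Replace the baseline sentence in SAP 6.4 with:

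*If the first-day value is missing, the last non-missing value before the first dose of study drug is used; if no pre-dose value exists, baseline is missing and the subject is left out of change-from-baseline analyses for that variable.*

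The cost is one sentence, which a further erratum could carry. A subject with no pre-dose value drops out of the change analysis, and of the baseline-adjusted MMRM, for that variable. In practice this falls on hepcidin, EPO and QOL. For Hb, eligibility already rests on two screening measurements (inclusion criteria 5 and 6), so an eligible subject has a pre-dose value. A screening substitute may be up to 42 days old, which is a limitation, but it is still a pre-treatment value.

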## 6.5 Handling of clinical laboratory test values not more than the limit of quantification, etc

If the measured values are reported to be not more than the limit of quantification, less than the limit of quantification, or impossible to calculate, the following handling procedures should be applied for tabulation, and missing values or zero values should not be used..

[Handling of quantification limit values]

- (1) If the measurement is reported as less than the limit of quantification

The value obtained by adding the following processing to the limit of quantification value is used as an alternative value for tabulation.

- 1) After checking the number of significant figures of the applicable item, 1 should be subtracted from the lowest significant figure of the reported quantification limit value.
- 2) It should then be expanded by one digit to a smaller number and 9 is set.

Example) Report: <3      Significant figure from the measuring facility: up to ones digit

→      Tabulation handling: 2.9

Report: <500      Significant figure from the measuring facility: up to tens digit

→      Tabulation handling: 499

- (2) When the measured value is reported as not more than the limit of quantification or not less than the upper limit of quantification, the limit of quantitation itself should be used as a substitute value for tabulation.

Example) Not more than the limit of quantification

Report:  $\leq 10$  → Tabulation handling: 10

Not less than the limit of quantification

Report:  $\geq 20$  → Tabulation handling: 20

## 7. Statistical Method

### 7.1 Basic Matters

#### 7.1.1 Level of significance and confidence coefficient

When implementing tests, level of significance should be set at 2-sided 5%. Confidence interval (CI) will be 2-sided with a confidence coefficient of 95%.

#### 7.1.2 Descriptive statistics to calculate

Types of descriptive statistics to be calculated for each variable are provided below.

Number of subjects, mean, standard deviation (SD), median, minimum, maximum, and 2-sided 95% CI of the mean

#### 7.1.3 Number of digits displayed

The number of digits to be displayed in the analysis results will be as follows.

Numeric content	Number of display digits
p value	3 decimal places; however, when it is less than 0.001, it is described as "< 0.001".
Proportion (percentage)	Integer part + 1 decimal place
Rate of change	Integer part + 1 decimal place
Descriptive statistics (minimum and maximum)	Same as the number of digits as original variable
Descriptive statistics (mean, SD, median)	Number of digits of the original variable + 1 digit
Rate of increase in Hb value	Integer part + 4 decimal places
QOL (EQ-5D-5L) index value	Integer part + 3 decimal places

Hepcidin will be measured in units of pg/mL; however, the unit used for tabulation should be ng/mL, and the number of displayed digits should be three decimal places.

### 7.2 Breakdown of subjects

#### 7.2.1 Disposition

For subjects enrolled in the treatment period, the breakdown of each analysis set should be provided.

Items: Number of subjects enrolled in the treatment period, number and proportion of subjects in the FAS, number and proportion of subjects not included in the FAS, number and proportion of subjects in the safety analysis set, number and proportion of subjects not included in the safety analysis set

### 7.2.2 Subjects who discontinued or interrupted their treatment

For subjects enrolled in the treatment period, the number and proportion of subjects who discontinued treatment should be calculated by reasons of discontinuation.

Item: Number and proportion of discontinued subjects who enrolled in the treatment period and the number and proportion of subjects who discontinued by reasons of discontinuation.

For subjects enrolled in the treatment period, the number of subjects with drug interruptions should be calculated by reasons for drug interruption. The denominator of the proportion should be the sum of the number of interruption operations. If there are multiple reasons for a single interruption, they should be counted for each reason and tabulated as the total number of interruption cases.

Item: Number and proportion of cases of interruption in subjects who enrolled in the treatment period and the number and proportion of cases by reasons for drug interruption

## 7.3 Demographic and other baseline characteristics

For each analysis set, key demographic and other baseline characteristics are summarized. Frequency and proportion will be provided for discrete variables and descriptive statistics for continuous variables (no calculation of 95% CI of the mean). If the safety analysis set is the same as the FAS, the results for the former will not be presented.

Table 7.3 Demographic and other baseline characteristics

Category	Item	Type of variables
Subject background	Sex (male, female)	Dichotomous
	Age (years) as of informed consent	Continuous
	2 Categories: <65, ≥65	Dichotomous
	2 Categories: <75, ≥75	Dichotomous
	Duration of nephrogenic anemia (years)	Continuous
	3 Categories: <1, 1 to <5, ≥5	Ordinal
	Height (cm)	Continuous
	Dry weight (kg)	Continuous
	BMI (kg/m  )	Continuous
	2 Categories: <25, ≥25	Dichotomous
	Race	Polytomous
	3 Categories: not Hispanic nor Latino, Hispanic or Latino, Unknown	
	Ethnicity	Polytomous
3 Categories: Asian (Japanese), Asian (Other), Other		

Evaluation data	Hb value (g/dL) on the first day of the treatment period	Continuous
	3 Categories: <9, 9 to <10, ≥10	Trichotomous
	Liver function test (U/L) on the first day of the treatment period	
	3 Categories: AST and ALT both not more than upper limit of normal, either above the upper limit of normal and both ≤2 times the upper limit of normal, either >2 times the upper limit of normal	Trichotomous
	CRP (mg/dL) on the first day of the treatment period	Continuous
	Ferritin (ng/mL) on the first day of the treatment period	Continuous
	2 Categories: <100, ≥100	Dichotomous
	TSAT (%) on the first day of the treatment period	Continuous
2 Categories: <20, ≥20	Dichotomous	
Smoking status	Presence or absence of smoking status 3 Categories: never smoked, ex-smoker, current smoker	Polytomous
Underlying cause of CKD	Underlying cause 8 Categories: diabetes mellitus, hypertension, autoimmune/glomerulonephritis/vasculitis, interstitial nephritis/pyelonephritis, cystic/hereditary/congenital disease, neoplasm/tumor, unknown, other	Polytomous
Complication	Presence or absence of complications on the first day of the treatment period	Dichotomous
	Presence or absence of hypertension	Dichotomous
	Presence or absence of diabetes mellitus	Dichotomous
	Presence or absence of dyslipidemia	Dichotomous
Iron supplement	With or without iron supplements on the first day of the treatment period	Dichotomous
	2 Categories: oral, intravenous	Dichotomous
Iron-containing phosphate binders	With or without iron-containing phosphate binders on the first day of the treatment period	Dichotomous
Previous ESA formulation	ESA formulation washout (yes/no)	Dichotomous
Hemodialysis	Types of hemodialysis 2 Categories: hemodialysis, hemodiafiltration	Dichotomous
	Duration of hemodialysis (years)	Continuous
	Frequency of dialysis 2 Categories: 3 × per week, other	Dichotomous

